3.3.2. Secondary Endpoints

Duration of Objective Response: length of time from the date of first evidence of response (CR or PR) to date of first evidence of PD or death. Patients who did not experience progression or death will be censored at the time of last contact (on the long-term follow-up date or the end of study date, whichever is later).

Duration of Stable Disease: length of time from the date of first evidence of response (CR, PR or SD) to date of first evidence of PD or death. Patients who did not experience progression or death will be censored at the time of last contact (on the long-term follow-up date or the end of study date, whichever is later).

Progression-Free Survival: length of time from the date of first administration of study drug to the date of first evidence of disease progression or death. Patients who did not experience progression or death will be censored at the time of last contact (on the long-term follow-up date or the end of study date, whichever is later).

Overall Survival: length of time from the date of first administration of study drug to the date of death from any cause. Patients who did not experience death will be censored at time of last contact (on the long-term follow-up date or the end of study date, whichever is later).

Duration of response, duration of stable disease, progression-free survival, and overall survival will be estimated using Kaplan-Meier product limit estimates and the estimated median and 90% confidence interval of the time-to-event.

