Statistical methods: Safety Endpoint Analyses: 
Safety endpoints for AEs include the following: incidences of all treatment-emergent adverse events (TEAEs) and all serious adverse events (SAEs); number and incidence of TEAEs and SAEs by severity; number and incidence of TEAEs and SAEs by relationship to study drug; number and incidence of all Grade 3 and 4 TEAEs and by severity and relationship to study drug; and discontinuation of patients from the study due to AEs or death. Safety endpoints for AEs, clinical laboratory tests, vital signs, ECG, and physical examination findings will be specified in the statistical analysis plan. Physical examination findings and ECGs will be listed. All other safety data will be summarized using descriptive statistics.
 Efficacy Endpoint Analyses: 
Response rates will be summarized using number and percentage of patients with a best response of CR, PR, SD or PD assessed by RECIST v 1.1 across all time points. For duration of response, duration of stable disease, PFS and OS, the Kaplan-Meier product-limit method will be used to estimate the median survival. Patients who do not have disease progression will be censored at the time of last contact.
 
Progression-free survival will be calculated from the date of first treatment to the date of progression or death.
 
Overall survival will be calculated from the date of first treatment to the date of death from any cause; patients who do not experience death will be censored at the time of last contact.
 
SAS Version 9.4 or higher for Windows (SAS Institute, Cary, NC) or higher will be used for all analyses.
 Pharmacokinetic and Pharmacodynamic Endpoint Analyses: Analysis plans will be described in the written plans provided by the laboratories performing the analyses.	

CONTENTS

2	SYNOPSIS	3
3	LIST OF ABBREVIATIONS.....	14
4	INTRODUCTION	17
4.1	FF-10502-01 Background	17
	Figure 1. Chemical Structure of FF-10502-01	18
4.2	ZK 820973 Preclinical Summary	18
4.2.1	ZK 820973 Preclinical Pharmacokinetics, Distribution, Metabolism, Excretion	18
4.2.2	ZK 820973 Preclinical Safety Pharmacology.....	19
4.2.3	ZK 820973 Genetic Toxicology	19
4.3	FF-10502-01 Preclinical Studies	19
4.3.1	FF-10502-01 In Vitro Anti-tumor Activity	19
	Table 1. Growth Inhibition of FF-10502-01 and Gemcitabine in Human Tumor Cell Lines ..	20
4.3.2	FF-10502-01 In Vivo Anti-tumor Activity.....	20

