Blood samples for PK assessment of FF-10502 plasma concentrations for patients in Cohort 13 will be collected on Cycle 1 Days 1 and 8, pre-dose, immediately following cessation of infusion (within 15 minutes), between 1-2 hours post-infusion, and between 4-6 hours post-infusion. Incorporation of FF-10502 into the cellular DNA of whole blood will be assessed as a pharmacodynamic endpoint pre-dose on Cycle 1 Days 1 and 8; and at any time during the Cycle 1 Day 15 visit. Blood for hematology and serum chemistry determinations will be collected within 28 days before Cycle 1 Day 1, on Days 1, 8, and 15 of Cycle 1, on Day 1 of each subsequent cycle, and at End of Treatment. After Cycle 1, blood for hematology also will be collected pre-dose on Day 8 of each cycle. Urine will be collected for urinalysis within 28 days before Cycle 1 Day 1, on Day 1 of each cycle, and at the End-of-Treatment Visit.

All Cohorts (Both Phases):

Disease assessments, based on computed tomography (CT) and/or magnetic resonance image (MRI), will be obtained at Week 8 and every 8 weeks thereafter until documented progression of disease (PD) for Cohorts 1 to 12; and at Week 6 and every 6 weeks thereafter until documented PD for Cohort 13. Patients who demonstrate clinical benefit will be allowed to continue therapy with FF-10502-01 until progression of disease, observation of unacceptable adverse events, intercurrent illness or changes in the patient's condition that prevents further study participation.

Safety will be assessed through the monitoring of AEs, clinical laboratory parameters (hematology, serum chemistry), vital sign measurements, and physical examinations. Adverse events will be classified according to the Medical Dictionary for Regulatory Affairs (MedDRA) and graded according to the National Cancer Institute Common Terminology Criteria for Adverse Events (NCI CTCAE) version 4.03.

Efficacy assessments for solid tumors will be made according to the Response Evaluation Criteria in Solid Tumors (RECIST v. 1.1)¹.

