8.3 Treatment Duration

Treatment will continue until confirmation of disease progression, unacceptable toxicity, or patient decision to discontinue therapy.

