9.5 Long-term Follow-up

Long-term follow-up will consist of a clinic visit or telephone call every 3 months until death or patient's refusal to participate to assess survival.

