10.2.4 Timing of Assessments to Determine Response

Disease assessments will be made at the end of Cycle 2 and every two cycles thereafter. Disease assessments may be made at other time points at the discretion of the Investigator.

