11.3.2.2 Secondary Efficacy Endpoints

Duration of response, duration of SD, PFS and OS curves will be estimated by disease cohort using Kaplan-Meier product limit estimates. Median and 90% confidence interval of time-to-event will be estimated. Progression-free survival will be calculated from the date of first dose of study drug to the date of first documented evidence of disease progression or death, whichever is earlier. Overall survival will be calculated from the date of first dose of study drug to the date of death due to any cause. Patients who did not experience progression or death will be censored at the time of last contact.

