APPENDIX D. Schedule of Study Procedures

Table 6: Schedule of Procedures for Cohorts 1-12

Study Activity	Screening ¹	Treatment Cycle 1				Treatment Cycles After 1				Progression/ Relapse	EOT ²	Long-term FU ³
		D1	D8 ⁴	D15 ⁴	D22 ⁴	D1 ⁵	D8	D15	End of C2 ^{6,7}			
Signed ICD	X											
Medical history	X											
Physical examination	X	X ⁸				X ⁸					X	
Vital signs	X	X	X	X	X	X					X	
ECOG PS	X	X				X					X	
Height	X											
Weight	X	X				X					X	
Hematology ⁹	X	X	X	X	X	X	X	X			X	
CD4, CD8, and B-cell counts		X				X					X	
Coagulation	X											
Serum chemistry ¹⁰	X	X	X	X	X	X					X	
Urinalysis ¹¹	X	X				X					X	
β-hCG (WCBP)	X											
12-lead ECG	X										X	
Concomitant medications	X	Continuous										
AE assessment		Continuous										
Disease response assessment ¹²	X								X	X		
Blood for PK assessment ¹³		X		X								
Blood for PD assessment ¹⁴		X	X	X	X							
FF-10502-01 administration ¹⁵		X	X	X		X	X	X				

Study Activity	Screening ¹	Treatment Cycle 1				Treatment Cycles After 1				Progression/ Relapse	EOT ²	Long-term FU ³
		D1	D8 ⁴	D15 ⁴	D22 ⁴	D1 ⁵	D8	D15	End of C2 ^{6,7}			
Survival assessment		X	X	X	X	X	X	X	X	X	X	X
Tumor biopsy		X ¹⁶										

Abbreviations: AE, adverse event; β -hCG, beta human chorionic gonadotropin; C, cycle; CT, computed tomography; D, day; EDTA, ethylenediaminetetraacetic acid; ECG, electrocardiogram; ECOG PS, Eastern Cooperative Oncology Group Performance Status; EOT, end of treatment; FU, follow-up; ICD, informed consent documentation; MRI, magnetic resonance imaging; PD, pharmacodynamics; PK, pharmacokinetics; WBCP, women of childbearing potential.

¹ Screening to be performed within 28 days before Cycle 1, Day 1.

² End of Treatment visit should be 28 days from last dose of study drug (\pm 5 days).

³ Long-term follow-up consists of clinic visits or telephone calls every 3 months to assess survival status.

⁴ Day 8, 15, or 22 \pm 1 day.

⁵ Day 1 (window \pm 2 days).

⁶ Day 28 \pm 3 days.

⁷ And every 2 cycles thereafter.

⁸ Abbreviated physical exam.

⁹ Hematology collected at Screening, Cycle 1 Day 1 (only if not performed in the previous 72 hours), Days 8, 15 and 22, Day 1 of each subsequent cycle (within 3 days of Day 1 of each subsequent cycle), Day 8 and 15 of each cycle (pre-dose) and End of Treatment. See [Table 3](#) for tests to be conducted at each time point.

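### PFS, duration of response and duration of stable disease are censored at last contact, which can be a survival-only call, so unscanned time is counted as progression-free

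*SAP*

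**What the plan says.** **Censoring date.** SAP 3.3.2 applies one rule to duration of response, duration of stable disease and PFS: patients with neither event on record "will be censored at the time of last contact (on the long-term follow-up date or the end of study date, whichever is later". OS uses the same date. Protocol 11.3.2.2 has "Patients who did not experience progression or death will be censored at the time of last contact", and the efficacy paragraph of the synopsis has "Patients who do not have disease progression will be censored at the time of last contact".

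**What last contact can be.** Protocol 9.5: "Long-term follow-up will consist of a clinic visit or telephone call every 3 months until death" or refusal, for survival. The footnotes to the Appendix D schedules agree: "Long-term follow-up consists of clinic visits or telephone calls every 3 months to assess survival status". Tables 6 and 7 mark disease assessment at screening, at the end of Cycle 2 and every second cycle after that, and at progression or relapse. Nothing is marked under end of treatment or long-term follow-up.

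**When scans stop.** Here the documents pull in two directions. Protocol 6.1 says that scans "will be obtained at Week 8 and every 8 weeks thereafter until documented progression of disease (PD) for Cohorts 1 to 12", with a 6-week equivalent for Cohort 13, and SAP 1.3.2 repeats this. Protocol 10.2.4 instead ties scans to treatment cycles: "Disease assessments will be made at the end of Cycle 2 and every two cycles thereafter". The visit list in 9.2.2.4 and the two schedule tables do the same.

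**Leaving without progression.** Protocol 8.3: "Treatment will continue until confirmation of disease progression, unacceptable toxicity, or patient decision to discontinue therapy". Section 7.3.1 adds withdrawal of consent, noncompliance and investigator judgment.

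In the text available, neither document has a rule for the last evaluable tumour assessment, for missed scans or for new anti-cancer therapy.

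**The concern.** Last contact is the right censoring date for OS, because a telephone call does establish that the patient is alive. It does not establish that the tumour has not grown. Kaplan-Meier treats a censored patient as at risk and event-free up to the censoring date, so a later date than the last scan puts unobserved time into the risk set. Taking the later of two dates makes that time as long as possible.

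The same gap affects deaths. If a patient stops scanning and dies months later, the death is the PFS event at the death date, and the whole unscanned interval counts as progression-free.

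The three endpoints serve named secondary objectives, and Protocol 11.1 treats prolonged stable disease as possible benefit in Cohort 11. With a single arm, there is no control group carrying the same bias to offset it.

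**Working it through.** **1. No plan figure to reproduce.** The documents give no assumed PFS, number of events or drop-out rate. The figures below illustrate the rule; they do not predict the trial's results.

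**2. Inputs.** From the documents: 8-week scans (56/30.4375 = 1.84 months), 3-monthly contacts and 21 months' accrual. Minimum follow-up is 6 months by the text of Protocol 6.3, or 12 months from its totals (57 − 24 − 21 = 12), so both were run. Assumed: median time to progression 3 months, median survival after progression 5 months, exponential times, and early leaving independent of progression.

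**3. Model** (200,000 patients per scenario).
- Progression time P has hazard ln2/3. Death is P plus an exponential time with hazard ln2/5.
- The hazard of stopping scans is (ln2/3) × q/(1 − q), with q = 0.1, 0.2 and 0.3 the share stopping before true progression. This gives about 12%, 24% and 36% leaving before progression is detected.
- Follow-up is uniform from m to m + 21 months, with m = 12 or 6.
- Progression is recorded at the next scan on the grid, if the patient is still being scanned.

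**4. Kaplan-Meier 6-month PFS, m = 12.**

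| Leaving | Scans continue | Last contact (SAP) | Last scan, every death an event | Last scan, deaths after two missed scans censored there |
|---|---|---|---|---|
| 12% | 0.279 | 0.316 | 0.308 | 0.275 |
| 24% | 0.279 | 0.357 | 0.340 | 0.269 |
| 36% | 0.278 | 0.400 | 0.376 | 0.258 |

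With nobody leaving, the rules agree.

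**5. Splitting the excess.**
- Total (last contact minus continued scans): 3.7, 7.8 and 12.2 points.
- Censoring date alone (last contact minus last scan, every death an event): 0.8, 1.7 and 2.4 points.
- Still left after moving only the date: 2.9, 6.1 and 9.8 points. The missed-scan rule removes this, so it comes from late deaths.

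The date matters less because few leavers are still alive at cut-off. At 24% leaving they are 4.8% of all patients, or 0.048/0.241 = 20% of leavers.

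**6. Shorter follow-up (m = 6).** More leavers are alive at cut-off, so the date matters more. Last contact gives 0.314, 0.354 and 0.398. Last-scan censoring with every death an event gives 0.298, 0.321 and 0.349. The differences are 1.6, 3.3 and 4.9 points, that is about 3 to 5 points once roughly a quarter or more leave.

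**7. Median.** It is 3.7 months under every rule at 12% and 24% leaving. At about 36%, last contact gives about 5.0 months against 3.7 with continued scans.

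**8. Wider inputs.** These were median progression 2.5 or 4 months, survival after progression 5 or 8 months, 10% to 40% stopping before true progression, and m = 6. Last contact raises 6-month PFS by about 2 to 24 points over continued scanning, of which the date alone accounts for about 1 to 10. The median moves only at 40% stopping. Leavers alive without recorded progression are credited on average 8 to 11 months beyond their last scan.

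**The case against.** **Scanning may continue off treatment.** Protocol 6.1 and SAP 1.3.2 say scans run until documented progression, and the schedules have a progression/relapse assessment. If sites scan every patient on that basis, few are affected. This stands as a limit on size, and a reader should not infer that off-treatment scanning is ruled out. But the visit list, section 10.2.4 and both tables provide no off-treatment scan visit. The censoring rule should not depend on which text a site follows.

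**The date is not the main driver.** A reader might attribute the full 4 to 12 points to the censoring date. The calculation does not support that: with 12 months' follow-up the date accounts for about 1 to 3 points. Moving the date alone at 24% leaving still gives 0.340 against 0.279. This objection stands, and it shapes the fix.

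**The planned summary barely moves.** The plan reports a median with a 90% confidence interval, not a 6-month rate. The median is unchanged at 12% and 24% leaving. This also stands, although the upper part of the planned Kaplan-Meier curves and any rate read from them would still be affected.

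**These are secondary descriptive endpoints.** The primary objective is safety and dose, the primary efficacy endpoint is objective response, and SAP 2.4.2 plans no formal tests. The documents cite no PFS benchmark. This lowers the priority but does not make the rule right.

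**Conclusion.** Wrong as written; it should be fixed, but it does not put the trial's main conclusions at risk. The last-contact rule biases PFS and both duration endpoints upward, and no other passage corrects it.

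Under the stated assumptions, 6-month PFS is raised by about 4 to 12 points for 12% to 36% leaving. About 1 to 3 points come from the censoring date with 12 months' minimum follow-up, and about 3 to 5 with 6 months and a quarter or more leaving. Most of the rest comes from late deaths. The share leaving early is an assumption, and so is the absence of off-treatment scans. Only PFS was simulated; for the two durations the direction follows from the same rule, but their size was not estimated.

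A reader might infer that the response rate or the Cohort 11 and 13 decisions are compromised, or that median PFS is bound to be inflated. Neither follows. Objective response and the Simon boundaries do not use this date, and the median moves only when more than about a third leave early.

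**What to change.** In SAP 3.3.2, Protocol 11.3.2.2 and the synopsis:

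1. For PFS, duration of response and duration of stable disease, censor patients without progression or death at the last evaluable tumour assessment, or at first dose if there is none.
2. Pre-specify that a death or progression after two or more consecutive missed scheduled assessments is censored at the last evaluable assessment. Report alongside it the version in which every death is an event. Both are useful: in the illustration the missed-assessment rule falls 0.4 to 2.0 points below continued scanning, and the every-death version lies 2.9 to 9.8 points above it.
3. State how new anti-cancer therapy is handled.
4. Keep last contact for OS only.
5. Reconcile the text on scanning until progression with the cycle-based visit lists and schedule tables. Item 1 is safe under either reading.
6. While editing, reconcile the duration definitions. Protocol 10.2.3.2 ends both durations at progression only, whereas the SAP adds death. The protocol starts duration of stable disease at first dose, whereas the SAP starts it at first CR, PR or SD.

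The cost is text and one derivation, because scan dates are already collected. Reported PFS and durations may be less favourable.

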10.2.3.2 Secondary Efficacy Endpoints

Duration of Response: length of time from the date of first evidence of response (CR or PR) to date of first evidence of PD

Duration of SD: length of time from the date of the first administration of study drug to the date of first evidence of PD

Progression-Free Survival: length of time from the date of first administration of study drug to the first objective evidence of disease progression or death, whichever is earlier

Overall Survival: length of time from the date of first administration of study drug to the date of death from any cause

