Stable disease for ≥ 4 cycles (approximately 4 months) may also be of clinical benefit in this population. If the proportion of patients in this cohort having stable disease is $\geq 30\%$ after 25 patients have been enrolled and treated, enrollment into this cohort may continue until 50 patients are treated. Note that recruitment will continue past 25 patients—it will not stop until a decision is made at the interim analysis.

Cohort 12 (gallbladder carcinoma) is exploratory with 10 patients to be recruited. If the response rate amongst these patients is 26%, there will be a less than 5% chance of failing to see a response in at least 1 patient.

Cohort 13 (urothelial carcinoma) will also employ a Simon 2-stage design with 80% power, a 1-sided type I error of 5%, $p_1 = 20\%$ and $p_0 = 5\%$. If after 15 patients have been recruited, there are no responses, enrollment for this cohort may be suspended for futility. If after 27 patients have been recruited, 4 or more responses are observed, the null hypothesis of a 5% response rate will be rejected.

In both Cohorts 11 and 13, there will be no pause in recruitment prior to the interim analysis given the previous responses already observed in these indications. Furthermore, prior to any

decision to stop recruitment into a given cohort, the number of patients with prolonged stable disease will also be considered.

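### Duration of stable disease starts at first dose in the protocol but at the first scan showing CR, PR or SD in the SAP; its event and population also need one definition.

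*SAP*

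**What the plan says.** Duration of response and duration of SD are together a secondary objective (Protocol 5.2, SAP 1.2.2).

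- **Protocol 10.2.3.2:** "Duration of SD: length of time from the date of the first administration of study drug to the date of first evidence of PD". The companion endpoint reads "Duration of Response: length of time from the date of first evidence of response (CR or PR) to date of first evidence of PD". Neither sentence mentions death, and the SD sentence sets no limit by best response.
- **SAP 3.3.2:** duration of SD is the "length of time from the date of first evidence of response (CR, PR or SD) to date of first evidence of PD or death". Duration of response in the same section also ends at progression or death. PFS there starts at first dose. All these endpoints are summarised by a Kaplan-Meier median with a 90% confidence interval.
- **Scan timing, Protocol 6.1:** disease assessments "will be obtained at Week 8 and every 8 weeks thereafter until documented progression of disease (PD) for Cohorts 1 to 12". Cohort 13 follows a six-weekly grid instead, its first scan falling at Week 6.
- **Use of SD in Cohort 11, Protocol 11.1:** "Stable disease for ≥ 4 cycles (approximately 4 months) may also be of clinical benefit in this population". The section adds that enrolment may go on if at least 30% have SD once 25 patients are treated. It gives no start date for the SD count and does not refer to the endpoint in 10.2.3.2.
- **Censoring in the protocol:** the synopsis (efficacy endpoint analyses) censors patients without progression at last contact. Section 11.3.2.2, which covers both durations, PFS and OS together, censors those with neither progression nor death.

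**The concern.** The two documents describe different variables under one name. SD can be documented only at a scan, so the SAP clock cannot start before the first evaluable scan, whereas the protocol clock starts at first dose. The end of the interval differs as well: progression only in Protocol 10.2.3.2, progression or death in the SAP. The SAP also starts the SD clock for patients with CR or PR, so a responder contributes to both duration analyses.

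At stake is the reported median for a secondary objective. If the mismatch stays, the choice between the two definitions could be made after the data are seen. Protocol 11.1 also gives SD a role in deciding whether enrolment continues, without saying from when SD is counted.

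**Working it through.** **1. The plan's own figure.** Protocol 11.1 equates 4 cycles with about 4 months. With 28-day cycles, 4 × 28 / 7 = 16 weeks, and 112 / 30.4375 = 3.7 months, so the figure is reproduced. For Cohort 13, 4 × 21 / 7 = 12 weeks. Both match the response window in Protocol 11.3.2.1 and SAP 3.3.1, which count 4 cycles as 16 (or 12) weeks from first dose. The end of Cycle 2 is 2 × 28 / 7 = 8 weeks, or 2 × 21 / 7 = 6 weeks, which is the first scan.

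**2. Effect of the start date.** Take a patient whose first scheduled scan shows CR, PR or SD. Protocol duration = week of progression. SAP duration = week of progression − week of first scan.

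| Cohorts | Progression at | Protocol | SAP | Change |
|---|---|---|---|---|
| 1 to 12 | Week 16 | 16 wk | 8 wk | −50% |
| 1 to 12 | Week 24 | 24 wk | 16 wk | −33% |
| 1 to 12 | Week 32 | 32 wk | 24 wk | −25% |
| 13 | Week 12 | 12 wk | 6 wk | −50% |
| 13 | Week 18 | 18 wk | 12 wk | −33% |

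The gap is one scan interval, give or take the ±3-day scan window. It is larger if the first scan is not evaluable. A patient who progresses at the first scan never acquires a SAP start date.

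**3. From patient to median.** If the same patients are analysed with the same event, and all start at the first scheduled scan, every event and censoring time moves by the same constant. The Kaplan-Meier median and its limits then move by that constant too: 8 or 6 weeks. If the protocol endpoint is instead read as covering all patients, the two medians come from different sets of patients and need not differ by that amount.

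**4. Responders.** Suppose SD at Week 8, PR at Week 16 and progression at Week 32. The SAP gives duration of response 32 − 16 = 16 weeks and duration of SD 32 − 8 = 24 weeks, of which 16 were spent in response. The protocol sentence read literally gives 32 weeks, because it does not exclude responders either.

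**5. Death without progression.** Protocol 10.2.3.2: not an event for either duration. Protocol synopsis: censored, as a patient without progression. Protocol 11.3.2.2: not in the group to be censored, which implies an event. SAP 3.3.2: an event. The protocol does not agree with itself, and the SAP agrees with only one reading of it.

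**6. Design figures.** The decision rules for Cohorts 11 and 13 count responses, so no duration of SD enters them. For Cohort 11 (stop at 1 or fewer of 25, reject at 6 or more of 50), exact binomial sums give alpha 0.035 at 5% and power 0.807 at 16%, in line with the stated 5% and 80%. Neither figure depends on this definition.

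**The case against.** **A first-evidence start is defensible.** It mirrors duration of response in both documents. A first-dose clock, applied to patients selected for SD, gives each of them guaranteed event-free time up to the first scan. This stands: the choice of clock is a matter of preference, and the error is that the two documents differ.

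**The population is not a protocol-SAP contradiction.** This also stands. The SAP names responders and the protocol does not exclude them; both leave the population to be stated.

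**A reader might infer that the protocol censors deaths and so overstates both durations.** The documents do not settle this. Section 11.3.2.2 points the other way, and the SAP already counts death. It is an ambiguity to remove.

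**A reader might infer that the SAP clock would alter the Cohort 11 continuation decision.** On that clock a patient reaches 16 weeks only at Week 24, which is 6 cycles. But Protocol 11.1 names no clock and does not cite this endpoint. Its 30% sentence carries no duration, and its wording is permissive. SAP 2.4.6 plans no formal interim analysis. Nothing shows that the SAP variable would feed the count.

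The size of such an effect also depends on an assumed median. With exponential progression (medians not in the documents), the share qualifying is 2^(−t / median), at t = 16 weeks for the first-dose clock and t = 24 weeks for the SAP clock. Since 30% of 25 is 7.5, 8 patients are needed.

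| Assumed median | Week 16 | Week 24 | P(8 or more of 25), Week 16 vs 24 |
|---|---|---|---|
| 2 months | 28% | 15% | 0.397 vs 0.023 |
| 3 months | 43% | 28% | 0.903 vs 0.397 |
| 4 months | 53% | 38% | 0.989 vs 0.805 |
| 6 months | 65% | 53% | 1.000 vs 0.989 |

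The shares fall on opposite sides of 30% at only one of these four medians. In general this requires a median between 16 × ln 2 / ln(1/0.30) = 9.2 weeks (2.1 months) and 24 × ln 2 / ln(1/0.30) = 13.8 weeks (3.2 months). The shares also do not separate SD from response. This cannot be presented as a finding about the interim.

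**Conclusion.** The start-date contradiction is literal in the current text of both documents and should be corrected. Its size is about one scan interval per patient, 8 weeks in Cohorts 1 to 12 and 6 weeks in Cohort 13, for patients whose first scheduled scan shows CR, PR or SD. It does not apply to every patient, because those with progression at the first scan drop out of the SAP endpoint. A shift of the same size in the median assumes the same patients and the same event under both clocks.

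Two lesser points go with it: the population is not limited by best response in either document, and the protocol is inconsistent on death. The consequence is confined to a descriptive secondary summary. That the four-cycle SD count would have used the SAP clock is not shown; what the documents support is that its start date is missing.

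**What to change.** Put one definition in Protocol 10.2.3.2 and SAP 3.3.2:

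- **Start:** first dose for duration of SD, which aligns the SAP with the protocol.
- **Event:** progression or death, for both duration of SD and duration of response. Use one matching censoring sentence in the protocol synopsis and section 11.3.2.2.
- **Population:** patients whose best overall response is SD. Responders appear under duration of response only.
- **Caveat to print with the result:** these patients are event-free up to their first scan by selection.
- **Protocol 11.1:** state that SD of 4 or more cycles is counted from first dose, in line with the 16-week convention in Protocol 11.3.2.1 and SAP 3.3.1.

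The cost is a few definition sentences in the two documents and the reprogramming of one derived variable. No data collection or sample size changes.
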